9.4 Responsibilities

Chief Investigator (CI):

1. Checking for AEs and ARs when participants attend for treatment / follow-up.
2. Clinical oversight of the safety of patients participating in the trial, including an ongoing review of the risk / benefit.
3. Using medical judgement in assigning the SAEs seriousness, causality and whether the event was anticipated (in line with the Reference Safety Information) where it has not been possible to obtain local medical assessment.
4. Using medical judgement in assigning whether an event/reaction was anticipated or expectedness in line with the Reference Safety Information.
5. Immediate review of all SUSARs.
6. Review of specific SAEs and SARs in accordance with the trial risk assessment and protocol as detailed in the Trial Monitoring Plan.

7. Assigning Medical Dictionary for Regulatory Activities (MedDRA) or Body System coding to all SAEs and SARs.
8. Ensuring that all SAEs are recorded and reported to the sponsor within 24 hours of becoming aware of the event and provide further follow-up information as soon as available.
9. Ensuring that AEs and ARs are recorded and reported to the sponsor in line with the requirements of the protocol.
10. Expedited reporting of SUSARs to the MHRA and REC within required timelines.
11. Notifying Investigators of SUSARs that occur within the trial.
12. Checking for and notifying PIs of updates to the Reference Safety Information for the trial.

Sponsor:

1. Central data collection and verification of AEs, ARs, SAEs, SARs and SUSARs according to the trial protocol onto a database.
2. The unblinding of a participant for the purpose of expedited SUSAR reporting.

9.5 Notification of deaths

All deaths, including deaths deemed unrelated to the IMP, if they occur earlier than expected will be reported to the sponsor”.

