9 PHARMACOVIGILANCE

9.1 Definitions

Term	Definition
Adverse Event (AE)	Any untoward medical occurrence in a participant to whom a medicinal product has been administered, including occurrences which are not necessarily caused by or related to that product.
Adverse Reaction (AR)	An untoward and unintended response in a participant to an IMP which is related to any dose administered to that participant. The phrase "response to an IMP" means that a causal relationship between a trial medication and an AE is at least a reasonable possibility, i.e. the relationship cannot be ruled out. All cases judged by either the reporting medically qualified professional or the Sponsor as having a reasonable suspected causal relationship to the trial medication qualify as adverse reactions. It is important to note that this is entirely separate to the known side effects listed in the SmPC. It is specifically a temporal relationship between taking the drug, the half-life, and the time of the event or any valid alternative etiology that would explain the event.
Serious Adverse Event (SAE)	A serious adverse event is any untoward medical occurrence that: 
• results in death• is life-threatening• requires inpatient hospitalisation or prolongation of existing hospitalisation• results in persistent or significant disability/incapacity• consists of a congenital anomaly or birth defect Other 'important medical events' may also be considered serious if they jeopardise the participant or require an intervention to prevent one of the above consequences.

	
NOTE: The term "life-threatening" in the definition of "serious" refers to an event in which the participant was at risk of death at the time of the event; it does not refer to an event which hypothetically might have caused death if it were more severe.

Serious Adverse Reaction (SAR)	An adverse event that is both serious and, in the opinion of the reporting Investigator, believed with reasonable probability to be due to one of the trial treatments, based on the information provided.
Suspected Unexpected Serious Adverse Reaction (SUSAR)	A serious adverse reaction, the nature and severity of which is not consistent with the information about the medicinal product in question set out in the reference safety information:

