9.2 Operational definitions for (S)AEs

As the IMP has a well-known and well established safety profile, new or unreported AEs and ARs are not expected in such a small trial. All AEs and ARs will be recorded. Acute exacerbations are expected to occur in COPD patients and therefore will not be recorded as (S)AEs or ((S)ARs). Breaking the blind will only take place where information about the participant's trial treatment is clearly necessary for the appropriate medical management of the participant

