9.3 Recording and reporting of SAEs, SARs AND SUSARs

All SAEs / SAEs occurring from the time of written informed consent until 30 days post cessation of trial treatment must be recorded on the AE Form and emailed to the Sponsor ([contact]) within 24 hours of the research staff becoming aware of the event.

For each SAEs the following information will be collected:

- Full details in medical terms and case description
- Event duration (start and end dates, if applicable)
- Action taken
- Outcome
- Seriousness criteria
- Causality (i.e. relatedness to trial drug / investigation), in the opinion of the investigator
- Whether the event would be considered anticipated.

Any change of condition or other follow-up information should be emailed to the Sponsor as soon as it is available or at least within 24 hours of the information becoming available. Events will be followed up until the event has resolved or a final outcome has been reached.

All ARs/SARs/SUSARs occurring from the time of start of trial treatment until 30 days post cessation of trial treatment must be recorded on the AE Form and emailed to the Sponsor within 24 hours of the research staff becoming aware of the event.

For each AR/SAR/SUSAR the following information will be collected:

- Full details in medical terms and case description
- Event duration (start and end dates, if applicable)
- Action taken
- Outcome
- Seriousness criteria
- Causality (i.e. relatedness to trial drug / investigation), in the opinion of the investigator
- Whether the event would be considered anticipated.

Any change of condition or other follow-up information will be emailed to the Sponsor as soon as it is available or at least within 24 hours of the information becoming available. Events will be followed up until the event has resolved or a final outcome has been reached.

All SAEs assigned by the PI or delegate (or following central review) as both suspected to be related to IMP treatment and unexpected will be classified as SUSARs and will be subject to expedited reporting to the Medicines and Healthcare Products Regulatory Agency (MHRA). The CI/delegated team will inform the Sponsor, MHRA, the REC and Marketing Authorisation Holder (if not the sponsor) of SUSARs within the required expedited reporting timescales: fatal and life-threatening within 7 days of notification and non-life threatening within 15 days.

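### Section 9.5 puts an undefined timing condition on telling the sponsor about deaths; combined with the exacerbation exemption in 9.2, a fatal exacerbation might not be notified under any section

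*Combined protocol and SAP*

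**What the plan says.** Five neighbouring provisions in section 9 of the combined protocol and SAP bear on a death.

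- **9.1 Definitions.** An untoward occurrence is an SAE if it "results in death". Timing and expectation play no part.
- **9.2 Operational definitions.** "Acute exacerbations are expected to occur in COPD patients and therefore will not be recorded as (S)AEs or ((S)ARs". There is no exception for exacerbations that are fatal.
- **9.3 Recording and reporting.** "All SAEs / SAEs occurring from the time of written informed consent until 30 days post cessation of trial treatment must be recorded" and emailed to the sponsor "within 24 hours of the research staff becoming aware of the event". The details collected for each SAE include the investigator's opinion on causality.
- **9.4 Responsibilities.** The Chief Investigator's duties include "Ensuring that all SAEs are recorded and reported to the sponsor within 24 hours of becoming aware of the event". Again there is no exception for deaths.
- **9.5 Notification of deaths.** "All deaths, including deaths deemed unrelated to the IMP, if they occur earlier than expected will be reported to the sponsor". The section does not say what length of survival is expected, who makes the judgement, how quickly the report is due, or over what period the duty runs.

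**The concern.** The section that deals specifically with deaths is looser than the general SAE rule. Staff handling a death are likely to turn first to the section with that title, where they find a condition that 9.1, 9.3 and 9.4 do not contain.

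The obvious reassurance is that the SAE rule catches every death anyway. Section 9.2 weakens it: if a death is treated as the outcome of an exacerbation, the exemption removes the event from the SAE route, leaving 9.5 and its undefined condition.

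What is at stake is safety oversight. Section 9.1 allows the sponsor, as well as the reporting clinician, to judge whether an event may be due to trial medication. It cannot do so for a death it has not been told about. The causal question is a real one here: section 2 names acute respiratory infection as the main cause of exacerbations, and section 6.2 lists severe infection and respiratory failure among the contraindications to metformin.

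**Working it through.** The plan states no figure on this point and no arithmetic applies. The check is to follow each kind of death through the rules as written.

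**Inputs.** SAE definition (9.1); exacerbation exemption (9.2); SAE window, deadline and SUSAR route (9.3); Chief Investigator's SAE duty (9.4); death rule (9.5). Two other places were checked for a further route: monthly trial assessments (7.7) and follow-up after adverse reactions (9.9).

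**Tracing.** In-window means from consent to 30 days after the end of trial treatment. Early means judged to meet the condition in 9.5.

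| Death | SAE route (9.1, 9.3, 9.4) | Death rule (9.5) | Result |
|---|---|---|---|
| In-window, not an exacerbation, early | Required, 24 hours | Required, no deadline | Reported; deadlines differ |
| In-window, not an exacerbation, not early | Required, 24 hours | Condition not met | The sections disagree; reported if 9.5 adds to 9.3 |
| In-window, exacerbation, early | Removed by 9.2 | Required, no deadline | Reported, with no time limit |
| In-window, exacerbation, not early | Removed by 9.2 | Condition not met | No section requires a report |
| After the window, early | Outside the window | Required, no deadline | 9.5 may be the main duty |

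**Could another route catch the fourth row?**

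1. *SAR reporting (9.3).* The exemption states that exacerbations "will not be recorded as (S)AEs or ((S)ARs", so serious reactions are removed along with serious events.
2. *SUSAR reporting (9.3).* This starts from events already classed as SAEs. An event that 9.2 keeps out of that class does not enter it.
3. *Late reactions (9.9).* This concerns SUSARs, so the same limit applies.
4. *Chief Investigator's duty (9.4).* This covers SAEs and so depends on the same classification.
5. *Monthly visits (7.7).* Exacerbation data are collected for a secondary endpoint. That is trial data collection, with no duty to notify the sponsor of a death.

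None of these closes the fourth row. The third row is only partly covered: the sponsor is told, but the 24-hour limit and the 9.3 causality assessment do not attach.

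**The case against.** The strongest reply is that 9.5 overrides nothing. A reader might infer from it that early deaths are the sole deaths that go to the sponsor. The text does not say so. Section 9.3 stands in full, 9.4 repeats it without condition, and 9.5 can be read as an additional duty. That stands: on this reading every in-window death not due to an exacerbation is still reported within 24 hours, and for those deaths the fault is a confusing inconsistency rather than a hole.

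It can also be said that the gap comes from 9.2 more than from 9.5, and that 9.2 does not mention death, so an investigator could treat the death as an SAE separate from the exacerbation that led to it. That reading is open. So is the other, because the exemption is written to cover serious events and carves nothing out. A reporting rule should not depend on which reading the site adopts.

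Three stronger inferences are tempting and are not supported:

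- *That a fatal exacerbation is the commonest death to expect here.* Section 1 links exacerbations with mortality but gives no breakdown of causes of death, either in COPD or in the eligible population.
- *That a comparison of mortality between treatments would be distorted.* Mortality is not an endpoint (sections 3.4 to 3.7), and 9.5 governs notification to the sponsor, not whether the trial records a death. A CONSORT flow diagram is planned in 10.3.1.
- *That such a death would vanish from the trial.* The exacerbation may still appear in the endpoint data. The supportable claim is that it might not reach the sponsor as a safety event.

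**Conclusion.** Wrong as written. Section 9.5 sets an undefined condition, with no deadline, that is inconsistent with 9.1, 9.3 and 9.4. Together with 9.2 it leaves one category of death, a fatal exacerbation not judged early, for which no section requires a report to the sponsor. A second category, a fatal exacerbation judged early, is reported without a time limit.

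The gap rests on two assumptions: that the 9.2 exemption extends to the fatal outcome, which its wording permits but does not compel, and that the death is not judged early. The inconsistency between 9.5 and the SAE rule needs neither assumption.

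No number of affected deaths can be given, because the documents contain no death rate. With 40 participants planned, the importance lies in the seriousness of any single missed report, which later analysis cannot put right.

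**What to change.** Reconcile sections 9.1 to 9.5 as follows.

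1. In 9.5, delete the timing condition.
2. In 9.5, state that all deaths from consent to 30 days after the end of trial treatment, whatever the cause and whether or not expected, are reported to the sponsor as SAEs within the 24 hours already set in 9.3.
3. In 9.2, state that the exacerbation exemption does not apply to fatal events.
4. Section 9.5 has no time limit at present. Keep whatever duty it now carries for deaths the investigator learns of after the 30-day window, so that the new wording does not narrow it.

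The cost is a few sentences, handled through the amendment process in 13.10. It needs no new assessment, visit or sample, and the deadline and window are the protocol's own. The change deals with deaths alone; non-fatal serious exacerbations remain under the 9.2 exemption, which is a separate question for the sponsor.

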9.6 Pregnancy reporting

All pregnancies within the trial (either the trial participant or the participant's partner, with participants consent) should be reported to the Chief Investigator and the Sponsor using the relevant Pregnancy Reporting Form within 24 hours of notification

Pregnancy is not considered an AE unless a negative or consequential outcome is recorded for the mother or child/foetus. If the outcome meets the serious criteria, this would be considered an SAE

9.7 Overdose

An overdose will be defined as taking more than the study dose of medication as reported by the patient or from pill counts. It will be recorded as an AE or SAE. The CI will decide whether the patient will be withdrawn from the trial

9.8 Reporting urgent safety measures

If any urgent safety measures are taken the CI/Sponsor shall immediately and in any event no later than 3 days from the date the measures are taken, give written notice to the MHRA and the relevant REC of the measures taken and the circumstances giving rise to those measures.

9.9 The type and duration of the follow-up of participants after adverse reactions.

Any SUSAR will be reported to the Sponsor irrespective of how long after IMP administration the reaction has occurred until resolved.

9.10 Development safety update reports

'Reference Safety Information' in this study is section 4.8 of Metformin SmPC. The CI will provide (in addition to the expedited reporting above) DSURs once a year throughout the clinical trial, or as necessary, to the Competent Authority (MHRA in the UK), where relevant the Research Ethics Committee and the sponsor. The report will be submitted within 60 days of the Developmental International Birth Date (DIBD) of the trial each year until the trial is declared ended

10 STATISTICS AND DATA ANALYSIS

10.1 Sample size calculation

The primary outcome will be change in sputum glucose from baseline after treatment with metformin, measured using an enzymatic assay (AmplexRed®). The median glucose concentration in COPD subjects measured in our previous study was 1,007 µM (SD 733µM). Metformin reduced airway glucose by c.30% in studies carried out in mice. Therefore to detect a similar effect in humans would require 30 subjects with 90% power at 5% significance. We aim to recruit 40 subjects to account for possible withdrawals.

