3.3 Outcome measures/endpoints

3.4 Primary endpoint/outcome

The median concentration of glucose in sputum in COPD patients after 3 months treatment with metformin compared with 3 months of placebo.

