3.5 Secondary endpoints/outcomes

These will also be assessed in COPD patients after 3 months treatment with metformin compared with placebo.

- 1) Median glucose concentration measured in nasal SAM strips
- 2) Bacterial infection (sputum semi-quantitative culture)
- 3) Inflammatory markers measured in sputum
- 4) Number of COPD exacerbations
- 5) Quality of life/symptom scores
- 6) Lung function measured using spirometry

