3.7 Table of endpoints/outcomes

Objectives	Outcome Measures	Timepoint(s) of evaluation of this outcome measure (if applicable)
Primary Objective To determine the effect of metformin on sputum glucose in COPD patients	The median concentration of glucose in sputum in COPD patients after 3 months treatment with metformin compared with placebo.	3 months
Secondary Objectives To determine the effect of metformin on: 1) Nasal glucose 2) Bacterial infection 3) Inflammatory markers in sputum 4) COPD exacerbations 5) Quality of life and symptoms 6) Lung function	1) Median glucose concentration measured in nasal SAM strips 2) Bacterial infection (sputum semi-quantitative culture) 3) Inflammatory markers measured in sputum 4) Number of COPD exacerbations 5) Quality of life/symptom scores 6) Lung function measured using spirometry	3 months

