10.3.2 Primary outcome analysis

The primary endpoint (median sputum glucose in treated versus non-treated participants) will be analysed using a Mann-Whitney test. The post-treatment sputum glucose will also be compared with baseline glucose using Wilcoxon matched-pairs test. Similar methods will be used to analyse the secondary endpoints.

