10.3.3 Secondary outcome analysis

Same as for primary outcome

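### Section 10.1 words the primary outcome as change from baseline after metformin, while 3.4 and 3.7 define month-3 sputum glucose versus placebo; the added baseline test in 10.3.2 has no stated role, period or baseline

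*Combined protocol and SAP*

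**What the plan says.** Section 3.4 defines the primary endpoint as "The median concentration of glucose in sputum in COPD patients after 3 months treatment with metformin compared with 3 months of placebo". The table in 3.7 agrees: "The median concentration of glucose in sputum in COPD patients after 3 months treatment with metformin compared with placebo", with 3 months as the time point. The outcome statements in the trial summary and section 4 give the month-3 level on metformin and name no comparator, although both describe the design as placebo-controlled.

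Section 10.1 differs: "The primary outcome will be change in sputum glucose from baseline after treatment with metformin". It goes on to a sample size: "Therefore to detect a similar effect in humans would require 30 subjects with 90% power at 5% significance". It does not say for which variable that number was computed.

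Section 10.3.2 has two tests under the primary-analysis heading. The first is "The primary endpoint (median sputum glucose in treated versus non-treated participants) will be analysed using a Mann-Whitney test". The second is "The post-treatment sputum glucose will also be compared with baseline glucose using Wilcoxon matched-pairs test". Section 10.3.3 reads "Same as for primary outcome", which carries both tests to the secondary endpoints. Section 3.5 defines those endpoints against placebo: "These will also be assessed in COPD patients after 3 months treatment with metformin compared with placebo".

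The schedule in Appendix 2 has a sputum sample at the baseline of each arm, so each participant has two candidate baselines.

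**The concern.** A change from baseline on metformin and a month-3 level compared with placebo are different variables, and possibly different contrasts. Section 10.1 can be read in two ways:

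- **Reading (a):** an uncontrolled pre-post change on metformin. It contains the drug effect plus any shift that would also have occurred on placebo, and cannot separate the two.
- **Reading (b):** a metformin-versus-placebo comparison of changes. This is a randomised contrast, but not the variable in 3.4, and its sample size can differ.

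Reading (a) has a matching test in 10.3.2. If the placebo contrast were null and the baseline test significant, the literal wording of 10.1 would allow the latter to be reported as the primary result. Section 2 says that a demonstrated reduction would justify a later trial with exacerbations as the outcome, so what counts as a demonstration matters.

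**Working it through.** **1. The definitions side by side**

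| Place | Variable | Time | Comparator |
|---|---|---|---|
| 3.4, 3.7 | level (median) | 3 months | placebo |
| Summary, section 4 | level | 3 months | not named in the outcome statement |
| 10.1 | change from baseline | not given | not given |
| 10.3.2, first test | level (median) | not given | non-treated |
| 10.3.2, second test | post-treatment v. baseline | not given | baseline, which one not given |

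**2. The plan's N = 30**

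Inputs from 10.1: 1,007 µM, SD 733 µM, reduction about 30%, 90% power, 5% significance (two-sided assumed). The difference is 0.30 × 1,007 = 302.1 µM.

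Taking 733 as the SD of the paired difference (on the raw scale, a within-person correlation of 0.5):

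- n = [(1.960 + 1.282) × 733 / 302.1]² ≈ 62 by the normal formula, and 64 by the t-test.
- 30 pairs give 59% power (noncentrality 0.412 × √30 = 2.26).

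So 30 does not follow from the stated inputs. With SD of the difference = SD × √(2(1 − ρ)), 30 pairs reach 90% power on the raw scale only if ρ is about 0.77. On a log scale the difference is ln(1/0.7) = 0.357. The log-SD is 0.569 if 1,007 is the median, as stated, or 0.652 if it is a mean. At ρ = 0.5 these need 29 and 38; the ρ needed for n = 30 is about 0.48 and 0.60. None of these assumptions is in the plan.

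**3. Reading (b): how far the sample size depends on the variable**

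Let r_w be the correlation of baseline with month 3 within a period, and r_b the common correlation between periods.

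- Level contrast: variance 2s²(1 − r_b).
- Difference in changes from own-period baselines: variance 4s²(1 − r_w).
- Ratio: 2(1 − r_w)/(1 − r_b).

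Sample sizes for a paired t-test (level / difference in changes), all correlations equal to ρ:

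| ρ | log-SD 0.569 | log-SD 0.652 | raw scale |
|---|---|---|---|
| 0.3 | 40 / 77 | 52 / 101 | 89 / 176 |
| 0.5 | 29 / 56 | 38 / 73 | 64 / 126 |
| 0.7 | 19 / 35 | 24 / 45 | 40 / 77 |
| 0.8 | 13 / 24 | 17 / 31 | 27 / 52 |

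The ratio of these is 1.8 to 2.0, but only because the correlations are equal. With r_w = 0.7 and r_b = 0.5 it is 2 × 0.3/0.5 = 1.2 (35 against 29 at log-SD 0.569). If one study-entry baseline serves both periods it cancels, and the ratio is 1.

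**4. Reading (a): a pre-post test under a common shift**

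The expected change on metformin is the drug effect plus the shift; in metformin minus placebo a shift common to both month-3 values cancels. Simulation: 20,000 trials, n = 30, half metformin first, equal correlation 0.5, lognormal data, signed-rank test at 5%, no drug effect, and a hypothetical one-off fall after entry. Percentage significant, log-SD 0.569 / 0.652:

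| Fall | Own-period baseline | Study-entry baseline |
|---|---|---|
| 10% | 7 / 7 | 16 / 13 |
| 15% | 11 / 9 | 32 / 25 |
| 20% | 16 / 14 | 53 / 43 |

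A paired metformin-placebo comparison stays near 5% throughout. The study-entry baseline does worse because the shift then enters every participant's change; with own-period baselines it enters only for those given metformin first. A rise would act the other way and mask a real reduction.

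**The case against.** The strongest reply is that 10.3.2 settles the matter. It gives the primary-endpoint label to the treated-versus-non-treated test and introduces the baseline test with the word *also*, which ordinarily marks an addition. That largely stands: a reader might infer from 10.1 that the trial's primary analysis is uncontrolled, and the documents as a whole do not support that. But an inference from one word is not a stated role, and 10.1 still names a different variable.

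It can also be said that this is an exploratory pilot. That lowers the stakes but does not remove the conflict: section 4 wants an effect size to power later trials, so the variable being estimated has to be fixed.

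The drift is invented. This is correct. Season is not a ready explanation because entry is spread over 12 months, and regression to the mean is not either, because eligibility does not select on sputum glucose. The percentages show a weakness of the design of that test, not an expected error rate in this trial.

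Two further inferences should be resisted. A reader might conclude that a change score always doubles the sample size; step 3 shows that it need not. A reader might also conclude from the schedule that the COPD assessment test (CAT) has no Arm 2 baseline. That row is blank at the Arm 2 baseline and month 1, but so is the adverse-event row, and 7.7 requires both assessments at monthly visits with the same procedures in the second period. A table or extraction fault is the likelier explanation.

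**Conclusion.** The conflict is on the face of the text and needs no assumption: 10.1 disagrees with 3.4 and 3.7, and the baseline test lacks a role, a treatment period and a baseline. It should be corrected before unblinding, while the choice cannot depend on results.

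Its numerical size is illustrative only. Under equal correlations a difference in changes needs about 1.8 to 2.0 times the n of the level contrast, falling to 1.2 or to 1 under other assumptions. Under a hypothetical fall of 10 to 20%, the pre-post test is falsely significant in 7 to 16% or 13 to 53% of trials, depending on a baseline the plan does not name. The documents do not show which variable N = 30 was computed for, so it cannot simply be reassigned to the 3.4 endpoint.

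**What to change.** 1. Replace the first sentence of 10.1 with the 3.4 definition (median sputum glucose after 3 months of metformin compared with 3 months of placebo). Use that same wording in the trial summary, section 4 and 10.3.2.
2. Recompute the sample size or power in 10.1 for that variable and for the analysis that will be used, stating the scale and the SD or within-person correlation. If 30 does not deliver 90%, restate the power. Do not merely assert that 30 refers to this variable.
3. In 10.3.2 and 10.3.3, state that comparisons with baseline are supportive only and are not evidence of a metformin effect. Name the treatment period and the baseline sample used.

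Cost: wording in five places and one recalculation. One test loses evidential status, and the stated power or sample size may become less favourable. Whether the Mann-Whitney test suits cross-over data is a separate question; it bears on item 2 only because the recalculation must match the chosen test.

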Therefore this study was the first to link elevated glucose in the lung to bacterial infection in COPD. Therefore reducing airway glucose has the potential to inhibit bacterial growth in COPD patients. One potential approach is to use the anti-diabetic drug metformin. In animal studies we have demonstrated that metformin decreases airway glucose and bacterial colonisation (4). The aim of the proposed study is to investigate whether metformin can achieve the same effects in COPD patients. Metformin is safe, cheap, does not cause hypoglycaemia and has been extensively used in COPD patients with diabetes with an excellent safety record (5). The primary aim of this study will be to evaluate the effects of metformin on lung glucose in COPD patients. If the study successfully demonstrates that metformin reduces airway glucose it will provide the data needed to justify a clinical trial of metformin with exacerbations as the primary outcome.

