4 TRIAL DESIGN

The proposed study will be a randomised, double-blinded, placebo-controlled, cross-over study of metformin in patients between the ages of 40 and 75 with a confirmed diagnosis of COPD. It will be an exploratory pilot trial, to gather preliminary information on the effects of metformin on sputum glucose and the feasibility of conducting a full-scale trial.

All subjects will have clinical assessments and blood, airway samples (nasal SAM and sputum) collected at baseline prior to the treatment phase. Clinical assessments will include lung function (FEV₁ and FVC), quality of life and symptom questionnaires (St George's Respiratory Questionnaire, COPD assessment test). Subjects will then either be commenced on metformin or placebo for a period of 3 months and blood, sputum and nasal samples collected at monthly intervals. Following a 2 week washout period the subjects will crossover to the other study arm for another 3 months and repeat samples collected.

Primary Outcome

The primary outcome will be sputum glucose measured using an enzymatic assay (AmplexRed® – ThermoFisher) after 3 months treatment with metformin. There is currently no data on which to base a power calculation and therefore this pilot study will assess what the size of any effect of metformin is in COPD subjects and thereby provide data that can be used to power any future, larger clinical trials.

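### The 30 subjects at 90% power in Section 10.1 do not follow from the stated inputs, do not describe the planned metformin-versus-placebo test, and conflict with Section 4

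*Combined protocol and SAP*

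**What the plan says.** Section 10.1 opens with "The primary outcome will be change in sputum glucose from baseline after treatment with metformin". It then gives its inputs: "The median glucose concentration in COPD subjects measured in our previous study was 1,007" µM, with an SD of 733 µM, and a reduction of about 30% observed in mice. From these it concludes "Therefore to detect a similar effect in humans would require 30 subjects with 90% power at 5% significance", and raises recruitment to 40 to cover withdrawals.

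Three other places bear on this figure.

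- Section 3.4 defines the primary endpoint as a comparison with placebo: "The median concentration of glucose in sputum in COPD patients after 3 months treatment with metformin compared with 3 months of placebo".
- Section 10.3.2 names the test: "The primary endpoint (median sputum glucose in treated versus non-treated participants) will be analysed using a Mann-Whitney test". A second test is against baseline, not placebo: "The post-treatment sputum glucose will also be compared with baseline glucose using Wilcoxon matched-pairs test".
- Section 4 states: "There is currently no data on which to base a power calculation".

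**The concern.** A sample size can be checked only if the reader knows the contrast, the test, the scale, the sidedness and the relevant SD. Section 10.1 gives an effect and a between-participant SD from an earlier study. For a cross-over, the quantity that matters is the SD of the within-participant difference, or equivalently the correlation between a participant's two values. Neither is given.

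The contrast is also unclear. Change from baseline on metformin could be tested within the metformin period alone or compared with placebo, and 10.1 does not say which. Section 3.4 is explicit that placebo is the comparator. If the 90% belongs to the baseline comparison, the plan states no power for its primary endpoint.

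This affects how the result will be read. Section 2 says: "If the study successfully demonstrates that metformin reduces airway glucose it will provide the data needed to justify a clinical trial". A non-significant result from a study described as having 90% power would be taken as evidence against an effect. That reading is justified only if the 90% belongs to the test and contrast actually used.

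**Working it through.** **Inputs (Section 10.1).** Level 1,007 µM; SD 733 µM; reduction 30%; power 90%; significance 5%. Forty recruited less a 25% loss leaves 40 × 0.75 = 30, so 30 is the number of completers planned for.

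**Effect.** δ = 0.30 × 1,007 = 302.1 µM; δ/SD = 302.1/733 = 0.412.

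**1. Attempt to reproduce 30 from the stated inputs (raw scale).**

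Paired, with the SD of the difference set to 733 (a correlation of 0.5 if both variances are equal): n = [733 × (1.960 + 1.282)/302.1]² ≈ 62. The exact calculation with the noncentral t gives:

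| Paired t-test | 90% power | 80% power |
|---|---|---|
| Two-sided | 64 | 49 |
| One-sided | 52 | 38 |

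Two independent groups, two-sided, 90% power: 125 per group by t-test, and about 130 per group for Mann-Whitney (dividing by its efficiency of 0.955 under normality). None of these is 30.

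**2. What has to be added to reach 30.**

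Raw scale: SD of difference = 733 × √[2(1 − ρ)]. Two-sided paired t-test:

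| ρ | n for 90% | Power, 30 completers | Power, 40 completers |
|---|---|---|---|
| 0.3 | 89 | 45% | 57% |
| 0.5 | 64 | 59% | 72% |
| 0.7 | 40 | 80% | 91% |
| 0.8 | 27 | 93% | 98% |

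Exactly 30 requires an SD of difference of 493 µM, that is ρ = 0.774.

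Log scale: effect = −ln(0.7) = 0.357. If 1,007 is a mean, log-SD = √ln(1 + (733/1,007)²) = 0.652. If it is a median, log-SD = √ln{[1 + √(1 + 4(733/1,007)²)]/2} = 0.569. Two-sided paired t-test:

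| Reading of 1,007 | n for 90% at ρ = 0.3, 0.5, 0.6 | Power, 30 completers, at ρ = 0.3, 0.5, 0.7 |
|---|---|---|
| Median | 40, 29, 24 | 80%, 91%, 99% |
| Mean | 52, 38, 31 | 69%, 82%, 96% |

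Untransformed Wilcoxon matched-pairs with a proportional effect on lognormal data (simulated), 30 completers, ρ = 0.3, 0.5, 0.6: 76%, 87%, 93% (median reading) and 63%, 77%, 85% (mean reading).

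**3. Power of the test named for metformin versus placebo.** Mann-Whitney applied to the two sets of cross-over values, two-sided 5%, simulated with ρ from 0 to 0.8:

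| Model | 30 completers | 40 completers |
|---|---|---|
| Normal, constant 302 µM reduction | 21–33% | 37–43% |
| Lognormal, 1,007 a mean, 30% proportional reduction | 52–57% | 65–79% |
| Lognormal, 1,007 a median, 30% proportional reduction | 63–77% | 77–93% |

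The normal model implies Φ(−1,007/733) = 8.5% negative concentrations. Its row is the lowest of the models tried and is not the expected case.

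Simulations used 20,000 replicates per setting and normal-approximation p-values. Lognormal correlations are on the log scale. All correlations and distributions are assumptions, because the plan gives none.

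**The case against.** The best defence is that 30 is reasonable for the contrast 10.1 appears to name. The section calls 1,007 a median and states the effect as a percentage, so a proportional effect on skewed data is a natural reading. On that reading a log-scale paired t-test needs 29 at a correlation of 0.5, and the Wilcoxon test that Section 10.3.2 plans against baseline has about 87% power at 30. The fault would then be an omission in reporting, not a wrong number. It can also be said that the low end of the Mann-Whitney range comes from an implausible model. With normal data and a proportional reduction, power at 30 is 39–42%. At 40 completers the most favourable lognormal setting reaches 93%. Finally, Section 4 may mean only that no human effect data exist, and the study is an exploratory pilot.

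Much of this is fair, and it is why the figure is called unsupported and not impossible. It does not rescue the 90%. The plan states neither the log scale nor the correlation, and the mean reading of 1,007 gives 38, not 29. The Wilcoxon test compares with baseline, so its power does not carry over to metformin versus placebo. Forty is enrolment before withdrawals, and at 30 completers Mann-Whitney fell short of 90% in every model tried. The pilot label does not reconcile a denial of any basis for a power calculation with an unqualified power claim.

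**Conclusion.** The concern holds, and the text must be corrected. The stated inputs do not yield 30 without an undocumented within-participant correlation, in some versions together with a log scale. For metformin versus placebo, the named test has roughly 20% to 80% power at 30 completers, against a stated 90%. The lognormal models, which avoid negative concentrations, put it at 52–77%. Sections 10.1 and 3.4 describe the primary outcome differently, and Sections 10.1 and 4 contradict each other on whether a power calculation is possible.

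The power ranges rest on assumed correlations of 0 to 0.8, equal variability under both treatments and the two distributional shapes shown. That the plan leaves its assumptions unstated, and that its sections disagree, depends on none of these. Whether Mann-Whitney suits a cross-over is a separate question; it matters here only because 10.1 does not give the power of the test the plan names.

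**What to change.** - Restate 10.1 for the within-participant metformin-versus-placebo comparison that will be used. Give the contrast, test, scale, sidedness and assumed within-participant SD or correlation, and say whether 1,007 is used as a median or a mean. If the sponsor holds the calculation behind 30, show it.
- Replace the unqualified 90% with a short table of power for 30 and for 40 completers, over assumed correlations of 0.3 to 0.8, on raw and log scales. Mark it as provisional because within-participant variability is unknown.
- Align the outcome sentence in 10.1 with Section 3.4.
- Reword Section 4 to say that there are no data on within-participant variability or on the effect of metformin on sputum glucose in COPD, so the power figures are provisional.

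The cost is a rewritten paragraph, one changed sentence and a small table. Enrolment stays at 40, with no added visits or assays. The stated power will look less favourable under several plausible assumptions.
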